7.1.3 Data Handling Rules

Unless otherwise noted, values reported as greater than or less than some quantifiable limit (e.g., "< 1.0") will be summarized with the sign suppressed in summary tables and figures, using the numeric value reported. Data will display on subject listings to include the sign.

7.1.4 Standard Calculations

Where appropriate, the calculated study day of each assessment or event will be presented with the assessment or event date on subject data listings, where study day will be determined as:

- The assessment/event date minus the date of first dose of study drug, if the assessment/event date is prior to the date of first dose; and
- The assessment/event date minus the date of first dose of study drug, plus one, if the assessment/event date is on or after the date of first dose.

Start and stop dates will be imputed when partial dates are present as needed to determine treatment emergent events and concomitant medications/procedures. No imputation will

be done for a completely missing start/stop date or for subjects who did not receive study treatment.

Start dates with a missing day but which have month and year provided will be imputed such that:

- If the provided month and year match the month and year for that subject's first dose date, then the Day 1 date will be used
- In all other cases the 1st of the month will be used with the provided month and year

Start dates with a missing day and month but which have year populated will be imputed such that:

- If the provided year matches the year for that subject's first dose date, then the first dose date will be used
- In all other cases the 1st of January will be used with the provided year

Stop dates will be imputed as follows:

- Missing day with a provided year and month will use the last day of the month
- Missing day and month with provided year will use December 31

If the imputed stop date is greater than the last study date for the subject, then the imputed date will be replaced with the last known subject date.

The date of the start of the current depressive episode and date of diagnosis of MDD will be imputed when the month or day are missing as follows:

- Missing day is set to 1 if the same year and month as the date of assessment. Otherwise it is set to 15
- Missing month and day are set to Jan 1 if the same year as the date of assessment. Otherwise it is set to July 1.

Other variables requiring calculations will be derived using the following formulas:

- **Days:** A duration between two dates expressed in days will be calculated using the following conventions:
 - Later date earlier date + 1, if the earlier date is on or after the date of first dose of study drug; or
 - Later date earlier date, if the earlier date is prior to the date of first dose of study drug.
- Months: A duration expressed in months will be calculated by dividing the duration in days by (365.25 / 12);

- Years: A duration expressed in years will be calculated by dividing the duration in days by 365.25;
- **Change from Baseline:** Change from baseline will be calculated as the post-baseline value minus the baseline value;
- **Percentage Change from Baseline:** Percentage change from baseline will be calculated as the change from baseline divided by the baseline value, multiplied by 100.

7.1.5 Baseline Definition

For efficacy and safety analyses presented by study visit, the baseline value will be defined as the last measurement prior to the start of study drug administration.

7.1.6 Multiple Comparisons/Multiplicity

The prespecified primary efficacy analysis will be conducted using a two-sided test at the α =0.05 level of significance. All other analyses will be also conducted with no adjustments for multiple comparisons.

7.2 Analysis Populations

The analysis populations are defined as follows:

- The Safety population is defined as all subjects who received study drug and will be used for summaries of safety parameters. Subjects will be analyzed according to treatment received.
- The Efficacy population includes all randomized subjects who received at least 1 dose of study drug, have a baseline HAMD-17 assessment total score, and have at least 1 post-baseline HAMD-17 assessment total score. Subjects will be analyzed according to randomized treatment assignment. This population will be used for the primary analysis and for all other efficacy analyses.
- The Per-Protocol (PP) population includes subjects in the efficacy population except those who experienced an important protocol deviation that is determined to substantially impact efficacy analysis, or did not have a HAMD-17 score at Week 8 analysis visit, or whose compliance at the end of the study was less than 70%. Subjects will be analyzed according to randomized treatment assignment. This population will be used for supportive efficacy analyses. The list of important protocol deviations for PP population will be classified by the sponsor before the final database lock and the unblinding of the study.

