7.3 Visit 3: Week 2 (Day 15)

The following order of procedures is recommended to prioritize safety and efficacy assessments:

- 1. Breathalyzer test for blood alcohol level
- 2. Subject and investigator will conduct/administer the following assessments on the tablet supplied:
 - a. Allow subject to complete HADS; reviewed by site personnel qualified to oversee completeness
 - b. C-SSRS 'Since Last Visit' version
 - c. CGI-I
- 3. Concomitant therapies review and reporting
- 4. AE reporting
- 5. Physical examination if indicated
- 6. Vital signs (respiratory rate, BP, and pulse [supine and standing]; temperature)
- 7. COWS
- 8. The subject-returned investigational study drug will be accounted for and subject will be reinstructed if found to be out of compliance
- 9. Complete IWRS
- 10. Blood and urine collection for central laboratory analysis (including urine drug screen for all subjects and urine pregnancy test for women of child-bearing potential). Note: blood and urine may be collected earlier in the visit.
- 11. Dispense allocated study drug and instruct subject on the importance of compliance and returning the dispensed bottle with any unused study drug at each visit.
- 12. Instruct all subjects to take 1 capsule of their assigned study drug daily in the morning and preferably with food.

The investigator will review the results of the central laboratory tests for safety in a timely manner prior to the next visit.

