9.2.2 Efficacy Population

The Efficacy population includes all randomized subjects who received at least 1 dose of study drug, have a baseline HAMD-17 assessment value, and have at least 1 post-baseline assessment. This population will be used to summarize the primary and other efficacy data.

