7.4 Efficacy Evaluation

7.4.1 Datasets Analyzed

All efficacy summaries will be produced on the Efficacy Population; select efficacy summaries (including HAMD-17, response rate of HAMD-17, subgroup analysis of HAMD-17 ($<22 \text{ vs} \ge 22$), SHAPS, CGI-I) will also be produced on the PP Population. A data listing of subjects excluded from the Efficacy Population or PP Population, to include the reason for exclusion, will be presented. All data listings will be listed for all randomized or treated subjects.

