7.7 Changes in the Conduct of the Study or Planned Analyses

There are no changes to the planned analyses described in the study protocol in this SAP.

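### The SAP requires a post-baseline HAMD-17 for every efficacy analysis, which the protocol does not say, so some early leavers' Week 2 HADS and CGI-I data drop out of those analyses

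*SAP*

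**What the plan says.** Protocol section 9.2.2 defines the Efficacy population as randomized subjects who took at least one dose and who "have a baseline HAMD-17 assessment value, and have at least 1 post-baseline assessment". The post-baseline condition names no instrument. On use, the same section says: "This population will be used to summarize the primary and other efficacy data".

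SAP section 7.2 repeats the dose and baseline conditions but requires that subjects "have at least 1 post-baseline HAMD-17 assessment total score". It then states: "This population will be used for the primary analysis and for all other efficacy analyses". SAP section 7.4.1 agrees: "All efficacy summaries will be produced on the Efficacy Population". The only other efficacy set is the Per-Protocol population, which is a subset of this one.

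SAP section 7.7 states: "There are no changes to the planned analyses described in the study protocol in this SAP". SAP section 4 says the same. The SAP addendum revises the baseline definition, an ophthalmology window, the compliance calculation and the LOCF rule, but not this population.

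**The concern.** The two definitions admit different subjects, and the difference is not declared. The SAP makes entry to the analysis of every efficacy scale depend on a scale that is first scheduled two weeks after HADS and CGI-I. Someone with valid Week 2 HADS and CGI-I values can be excluded from the analysis of those values because a different measurement was never taken.

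Whether that measurement is taken depends on what happens after randomization: who stops drug early, and who is still on drug when seen for the last time. If this differs between arms, the HADS and CGI-I comparisons are made on a selected set. A repeated-measures model can use a subject who has only a Week 2 value, and that value carries some information about later visits. Here the subject is removed before the model is fitted.

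**Working it through.** **Step 1. Who is admitted under each text**

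| Condition | Protocol 9.2.2 | SAP 7.2 |
|---|---|---|
| Randomized, at least one dose | required | required |
| Baseline HAMD-17 | required | required |
| Post-baseline condition | any assessment | HAMD-17 total score |
| Used for | primary and other efficacy data | primary and all other efficacy analyses |

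**Step 2. What is collected, and when** (schedules of procedures; protocol sections 7.3 and 7.4; SAP Table 3)

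| Scale | First post-baseline visit | First SAP window |
|---|---|---|
| HADS, CGI-I | Week 2 (Day 15) | Days 2 to 22 |
| HAMD-17, HAM-A, SHAPS | Week 4 (Day 29) | Days 16 to 43 |
| SDS | Week 4 (Day 29) | Days 23 to 36 |

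The Visit 3 list in protocol section 7.3 includes "Allow subject to complete HADS; reviewed by site personnel qualified to oversee completeness" and CGI-I, but no HAMD-17. SAP section 7.4.7 analyses HADS and CGI-I at each post-baseline visit, both by MMRM, with CGI-I improvement rates as well. Week 2 is therefore an analysed timepoint.

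**Step 3. Can such a subject arise?** Yes. Protocol section 5.5 requires discontinuation for low compliance over a 2-week interval, starting with Baseline to Week 2. Section 5.4 discontinues subjects who cannot tolerate the daily capsule. Under sections 7.6 and 7.8, an early leaver has efficacy ratings at the end-of-treatment visit only if they have remained on study drug. A subject can thus attend Week 2, stop drug, and never have a HAMD-17. That subject meets the protocol definition and fails the SAP definition.

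**Step 4. How many?** No figure in the plan depends on this point, so there is none to reproduce, and the documents give no early-dropout rate. Let *f* be the assumed share of the 180 randomized subjects with Week 2 HADS or CGI-I but no post-baseline HAMD-17. The number affected is 180 × *f*. If the loss is equal in both arms, the Week 2 standard error is multiplied by 1/√(1 − *f*).

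| Assumed *f* | 180 × *f* | SE multiplier |
|---|---|---|
| 1% | 1.8 (about 2) | 1.005 |
| 2% | 3.6 (about 4) | 1.010 |
| 5% | 9 | 1.026 |
| 10% | 18 | 1.054 |

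**Step 5. Could it bias the Week 2 comparison?** This is an illustration on assumed values. Let the Week 2 CGI-I improvement rate be 25% in stayers and 5% in leavers, and let leavers be 8% of the drug arm and 2% of the placebo arm.

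- Drug, all Week 2 data: 0.92 × 0.25 + 0.08 × 0.05 = 0.234
- Placebo, all Week 2 data: 0.98 × 0.25 + 0.02 × 0.05 = 0.246
- Difference: 0.234 − 0.246 = −1.2 percentage points
- SAP population: 0.25 − 0.25 = 0

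With leaver shares reversed, the difference is +1.2 points. With equal shares (5% in each arm), both rates are 0.95 × 0.25 + 0.05 × 0.05 = 0.24 and there is no shift.

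**Step 6. Does it carry to Week 8?** In an MMRM, a Week 2 value reaches Week 8 only through the within-subject correlation. Assume a correlation of 0.5, leavers 0.5 SD different at Week 2, and leaver shares of 10% and 5%. The Week 8 difference then moves by about 0.5 × 0.5 × (0.10 − 0.05) = 0.0125 SD, which is very small.

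**The case against.** The strongest reply is that the protocol sentence runs straight from the baseline HAMD-17 to the post-baseline assessment, so HAMD-17 may be meant in both places. Protocol section 9.1 also leaves full statistical detail to the SAP. On that reading the SAP only clarifies, and the no-changes statement is true. This is possible, and the documents do not show a deliberate departure. It answers the charge of an undeclared change. It does not answer the analytic point, because the HADS and CGI-I analyses would still be conditioned on another scale that is first scheduled later.

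Three further replies hold:

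- **The affected group is narrow.** A reader might take everyone who leaves before a first HAMD-17 as losing usable data. Some leave before Visit 3 and have no Week 2 data. Others have a HAMD-17 at an end-of-treatment visit while still on drug and stay in, since SAP section 7.2 ties the qualifying score to no visit.
- **Transparency is largely provided for.** SAP section 7.4.1 plans a listing of excluded subjects with reasons, section 7.3.1 gives population counts by arm, and section 7.1.1 lists collected data for all randomized subjects. The values are left out of the analyses, not out of the report.
- **The reach into later visits is small.** Under SAP section 7.1.1, percentages use subjects with available data, so a subject with only Week 2 data changes only the Week 2 CGI-I rate. Step 6 shows the same for the models.

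**Conclusion.** The discrepancy is real on the text, and the SAP does not declare it. Its consequence is limited to HADS and CGI-I, mainly at Week 2.

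A reader might infer that the primary result is at risk, or that every endpoint is affected. The documents support neither. The excluded subjects have no post-baseline HAMD-17 and so contribute no change score to the primary MMRM. HAM-A and SHAPS share the HAMD-17 schedule, SDS also starts at Week 4, and safety endpoints use the Safety population.

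The size cannot be derived from the documents. The range of about 2 to 18 subjects rests wholly on the assumed 1% to 10%. Bias arises only if leavers both differ from stayers and are unequally spread between arms, and its direction is unknown. This is an inexpensive improvement to two secondary analyses, not a threat to the trial's main conclusion.

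**What to change.** Reconcile protocol section 9.2.2 and SAP section 7.2 before unblinding. In the SAP, keep the post-baseline HAMD-17 requirement for the HAMD-17 analyses. For HADS and CGI-I, use the protocol wording, made explicit: randomized, dosed, with a baseline HAMD-17 and at least one post-baseline efficacy assessment. All available post-baseline values then enter the MMRMs and the CGI-I improvement rates.

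If the sponsor prefers the narrower set, SAP section 7.7 should declare it as a change (with section 4 corrected to match), and HADS and CGI-I should also be reported on the protocol population as a sensitivity analysis.

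The cost is one SAP sentence and one population flag. The downside is that N will differ slightly between endpoints. No new listing of exclusions is needed.

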7.3 Study Subjects

7.3.1 Disposition of Subjects

Subject disposition will be summarized for all subjects by treatment group and over all subjects combined. Summaries will include the number and percentage of subjects screened, randomized, in each analysis population, completing the treatment, completing the study, and discontinuing the study early by the primary reason for discontinuation. Subject disposition will also be summarized separately for each study site.

Subject completion status, date of study completion/discontinuation, study day of discontinuation, and reason for discontinuation will be listed. Inclusion and exclusion eligibility will be listed separately.

7.3.2 Important Protocol Deviations

Important protocol deviations will be summarized by treatment group and over all subjects combined for the Efficacy Population. Important protocol deviations are protocol deviations captured on-study that are deemed by the Sponsor to potentially impact the efficacy or safety conclusions of the study.

Important protocol deviation rules will be determined and appropriately categorized prior to database lock and prior to breaking the blind of the treatment group assignments. The number and percentage of subjects with any important protocol deviations as well as the number and percentage of subjects with deviations within each category will presented.

The important protocol deviations will be listed by treatment group and subject.

7.4 Efficacy Evaluation

7.4.1 Datasets Analyzed

All efficacy summaries will be produced on the Efficacy Population; select efficacy summaries (including HAMD-17, response rate of HAMD-17, subgroup analysis of HAMD-17 ($<22 \text{ vs} \ge 22$), SHAPS, CGI-I) will also be produced on the PP Population. A data listing of subjects excluded from the Efficacy Population or PP Population, to include the reason for exclusion, will be presented. All data listings will be listed for all randomized or treated subjects.

7.4.2 Demographic and Other Baseline Characteristics

Demographic variables including age, sex, ethnicity and race will be summarized by treatment group and over all subjects combined for the Safety, Efficacy, and PP Populations. Age at the time of informed consent, as collected on the eCRF, will be summarized using descriptive statistics. Sex, ethnicity, and race will be summarized with the number and percentage of subjects in each parameter category (including the number missing).

BlackThorn Therapeutics, Inc.	Statistical Analysis Plan
K2-MDD-201	Version 2.0; 03 June 2022

Baseline characteristics include height, weight, BMI, baseline CGI-S score, HAMD-17 score, SHAPS scores by both scoring methods, HAM-A score, HAMD-17 HADS subscale and total scores, HAMD-17 SDS total score, duration of current depressive episode, time since first diagnosis of depression, MDD medication use for the current episode of MDD prior to the start of study drug administration, nonpharmacological procedures for the current episode of MDD, and medical and psychiatric history other than MDD. Height, weight, BMI, baseline CGI-S score, HAMD-17, SHAPS scores by both scoring methods, HAM-A score, HAMD-17, SHAPS scores by both scoring methods, HAM-A score, HAMD-17, SHAPS scores, Sore, HAMD-17, SHAPS total and subscale scores, SDS total score, duration of current depressive episode, and time since first diagnosis of depression will be summarized using descriptive statistics by treatment group and over all subjects combined for the Safety, Efficacy, and PP Populations.

Medications for the current episode of MDD prior to the start of study drug administration will be coded using World Health Organization Drug Classification (WHODrug) for Drug Statistics Methodology (B3 Global) September 2019 version. For the MDD medication summary, the number and percentage of subjects receiving any medication will be summarized by treatment group, as will the number and percentage receiving any medication by Anatomical Therapeutic Chemical (ATC) drug class and generic drug name. Subjects reporting use of more than one medication at each level of summarization (any medication received, ATC class, and generic drug name) will be counted only once. ATC class terms will be displayed by descending order of incidence, as will generic drug names within each ATC class.

Medical and psychiatric history other than MDD will be presented only for the Safety Population. Medical and psychiatric history conditions will be coded using the Medical Dictionary for Regulatory Activities (MedDRA, version 22.1). Medical and psychiatric history will be summarized using frequency counts and percentages by treatment group, system organ class and preferred term.

All other baseline characteristics except MDD non-pharmacologic procedures will be summarized by treatment group and over all subjects combined for the Safety, Efficacy, and PP Populations. Demographic and baseline characteristic information will be listed for all randomized or treated subjects.

7.4.3 Measurements of Treatment Compliance

Percentage compliance to the study treatment regimen will be determined as the total dose actually taken divided by the expected dose received, multiplied by 100. The expected dose received will be calculated as (the date of last dose of study drug – the date of first dose of study drug + 1) x 1 capsule/day. If the date of last dose is not collected or missing, the date of last dose will be equal to the date of Visit 6/EOT or date of study completion/termination, whichever is earlier.

The total dose actually taken will be determined as the difference between the sum of all capsules dispensed before the date of last dose and the sum of all capsules returned. If number of capsules taken is not missing, the number of capsules returned will be

BlackThorn Therapeutics, Inc.	Statistical Analysis Plan
K2-MDD-201	Version 2.0; 03 June 2022

calculated as the number of capsules dispensed minus the number of capsules taken. If both the number of capsules returned and the number of capsules taken are missing, then it will be assumed that 0 capsules were returned. In addition, if the number of capsules dispensed is 0, then the corresponding number of capsules returned will be set to 0, if applicable.

Dosing compliance will be summarized using descriptive statistics, by treatment group, based on the Efficacy Population. As an exception rule, the compliance rate for subjects with < 14 days exposure duration will not be calculated, as the compliance may not be calculated reliably for such short duration. A subject is defined to be compliant if he/she has taken \geq 80% and <120% of the number of doses expected to be taken during the study overall. The number and percentages of subjects who are compliant and non-compliant within each treatment group will be summarized.

7.4.4 Primary Efficacy Endpoint Analysis Methods

The primary efficacy endpoint is the change from baseline to Week 8 on the HAMD-17 score. The estimand for the primary efficacy endpoint is the difference in means between treatment groups in the change of HAMD-17 scores from baseline to Week 8 for all subjects in the Efficacy population. For efficacy analyses, baseline is defined as the latest measurement prior to the first administration of study drug. The null hypothesis to be tested is that there is no difference between BTRX-335140 and placebo:

H₀:
$$\mu_A = \mu_{B_i}$$

Where μ_A and μ_B represent the mean values for BTRX-335140 and placebo, respectively. The alternate hypothesis to be tested is that the treatment group means differ:

H₁:
$$\mu_A \neq \mu_{B}$$
;

The analysis will be conducted using a mixed-models repeated measures (MMRM) with change from baseline in HAMD-17 score as the dependent variable and will include treatment group, week, and week by treatment group interaction as factors, and baseline HAMD-17 score as covariate. Variance estimation will be based on an unstructured covariance matrix. If the unstructured covariance matrix results in a lack of convergence, the heterogeneous autoregressive variance-covariance structure will be used.

The primary analysis will compare the groups at Week 8. The primary results obtained from the model will be the estimated treatment difference at Week 8. Significance will be assessed based on a two-sided test at the α =0.05 level of significance. In addition, the estimated treatment difference at Week 4 will be provided. The model-based least square (LS) means, standard errors, 95% CIs, and 2-sided p-values will be reported.

In addition, descriptive summary of HAMD-17 and each individual item will be generated by treatment group and by visit.

BlackThorn Therapeutics, Inc.	Statistical Analysis Plan
K2-MDD-201	Version 2.0; 03 June 2022

